Pharmacological Preconditioning With Desflurane in Liver Surgery

Last update: 30 April 2018, Thessaloniki, Greece

Study protocol

Objective

Ischemia-reperfusion injury is a major concern for hepatectomies. During hepatic resection the surgeon implements ischemia through inflow occlusion (Pringle maneuver) to prevent excessive and life threatening hemorrhage. Though, the pathophysiologic events occurring during ischemia are further promoted upon reperfusion. This entity may lead to liver failure and even Multiple Organ Disease Syndrome. Preconditioning has been identifying as a measure tackle ischemia – reperfusion injury in many organs. It refers to the exposure of a tissue at ischemic conditions to mitigate the subsequent reaction at re-exposure. Pharmacological preconditioning with the volatile anesthetic sevoflurane has been studied and proved beneficial for liver surgery. Our objective is to investigate the potential hepatoprotective role of another volatile anesthetic, desflurane. As sevoflurane has some properties that have been characterized as hepatotoxic, we have posed the hypotheses that desflurane may provide a beneficial advantage over ischemia – reperfusion injury.

Design

This is a randomized, double blind, clinical trial. Participants were allocated 1:1 using electronic software to receive either pharmacological preconditioning with desflurane (Group Desflurane, D) or no intervention (Group Control, C). 46 adult patients presented for elective hepatic excision of two or more liver segments, were recruited in the study. Informed consent was obtained by all patients. Exclusion criteria were presence of Hepatitis B, Hepatitis C or Human immunodeficiency virus infection, pregnancy, autoimmune disease, inflammatory bowel disease, liver cirrhosis, liver ablation therapy.

Methods

All patients were managed by the same surgical team and the same anesthesiologist. Only the anesthesiologist was aware of the group assigned to each patient. The surgeon was blinded as to the intervention and was asked to inform the anesthesiologist 30 minutes before the initiation of ischemia. At that point, the propofol infusion used to maintain anesthesia was substituted by desflurane to achieve pharmacological preconditioning for 30 minutes. After that interval, propofol infusion was reinitiated and desflurane ceased. Upon preoperative visit and at 30 minutes post reperfusion blood samples were taken for MMP 2, 9 and TIMP 1, 2 measurement. Specimens for histological test were taken before inflow occlusion and 30 minutes post reperfusion.

Statistical Analysis Plan

The SPSS v.22.0 software (SPSS, Inc., Chicago, Ill, USA) was utilized for all statistical analyses. . The significance level was set at $p \leq 0.05$ for the tested hypotheses. All data distributed normally according to Kolmogorov - Smirnov test. Independent samples T-test and independent samples Mann-Whitney test were performed for group (investigation and control) comparisons. The Fisher's Exact test and X^2 test were used for comparisons of groups relative to qualitative variables. Data for biological markers were explored within the frame of General Linear Models with the ANOVA method according to the model which involves one factor between patients (factor "Group" with two levels) and one factor within patients (factor "Time" with five levels, with repeated measures). Means' comparisons were done with the Least Significant Difference (LSD) criterion.

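### If all data were normal, why does the plan list a Mann-Whitney test beside the t-test?

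*Combined protocol and SAP*

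**What the plan says.** The Statistical Analysis Plan section makes four relevant statements.

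- Distribution: "All data distributed normally according to Kolmogorov - Smirnov test". No variable, arm or time point is excepted, and the version of the test is not given.
- Two-group comparisons: "Independent samples T-test and independent samples Mann-Whitney test were performed for group (investigation and control) comparisons". No variable is assigned to either test and no rule for choosing is stated.
- Categorical data: "The Fisher's Exact test and X^2 test were used for comparisons of groups relative to qualitative variables".
- Markers: "Data for biological markers were explored within the frame of General Linear Models with the ANOVA method", with Group between patients and Time within patients.

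The Methods section supplies the measurements. On blood it says "Upon preoperative visit and at 30 minutes post reperfusion blood samples were taken for MMP 2, 9 and TIMP 1, 2 measurement"; on tissue it says "Specimens for histological test were taken before inflow occlusion and 30 minutes post reperfusion". The scale of the histological result is not described.

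**The concern.** The usual reason to list a rank test beside a t-test is that some variables failed a normality check. Here the plan says none did, so the Mann-Whitney test appears without a reason. Either the normality sentence is too broad or the rank test was not needed on that ground.

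What would be at stake is freedom of choice. Two valid tests on the same data can fall on opposite sides of 0.05. If both were run on one variable and the smaller p-value reported, the false-positive rate would exceed the nominal level. The section is written in the past tense, so it cannot show that each choice was fixed before the data were seen. A related worry is that a Kolmogorov-Smirnov pass in a sample this small says little, so a blanket statement of normality may claim more than was shown.

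**Working it through.** **Step 1: the sentences side by side.** Categorical variables go to Fisher's exact or chi-square. Biological markers go to the Group by Time ANOVA. What is left for the t-test and Mann-Whitney is mainly the unnamed quantitative variables: baseline and operative data, and possibly the histological result. If that result is an ordinal score, a rank test is a natural choice. The plan does not say that it is. A single test per variable, with the two tests covering different variables, is the ordinary reading and is consistent with the text.

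**Step 2: is Mann-Whitney wrong if the data are normal?** The plan gives no figure to reproduce here.

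- Total sample: 46 (Design section).
- Allocation: "Participants were allocated 1:1 using electronic software", so 46 / 2 = 23 per arm is assumed; actual arm sizes are not stated.
- Level: 0.05 (Statistical Analysis Plan section); two-sided is assumed.
- Standardised difference for power: 0.85, assumed because it gives about 80% power.

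Simulated normal data, 20,000 trials:

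| Quantity | t-test | Mann-Whitney |
|---|---|---|
| Type I error | 5.0% | 4.9% |
| Power at 0.85 SD | 80.3% | 77.6% |

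The loss of power is 80.3 − 77.6 = 2.7 percentage points. Other runs, with and without continuity correction, put Mann-Whitney at 4.5% to 4.9% for type I error and 77% to 78% for power. Both tests hold their level, and the rank test is slightly less powerful.

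**Step 3: how often would the choice matter?** On normal data the two tests disagree about significance in about 2% of comparisons with no effect, 7.2% to 7.4% with an effect giving 50% power, and 5.4% to 5.7% with an effect giving 80% power.

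**Step 4: the worst case.** Suppose both tests were run on one variable and either result counted. The probability that at least one is significant is

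P(t or MW) = [P(t) + P(MW) + P(disagree)] / 2.

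With no effect this is (5.0 + 4.9 + 2.0) / 2 = 5.95%, which agrees with the directly simulated 6.0%. The inflation is therefore about one percentage point per comparison, and only under a practice that the document does not describe.

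**Step 5: the normality check.** For a single sample of 23 from an assumed lognormal distribution with log-scale SD between 0.3 and 1.0, the uncorrected Kolmogorov-Smirnov test rejects in 0.2% to 26% of samples, and the Lilliefors-corrected version in 17% to 84%. A pass on one variable can therefore be weak evidence. But the lognormal shape is an assumption, nothing in the document indicates a skewed variable, and no stated rule makes the choice between the t-test and Mann-Whitney depend on this check.

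**The case for a change.** The strongest case for acting is that this short section is the whole analysis plan. Nothing else in the document says which quantitative variables were compared by which test, and neither the categorical sentence nor the marker sentence explains the rank test. Naming the variables would take a line or two and would make each p-value traceable. The normality statement is also loose: the version of the test, the time points and the pooling of arms are unstated, and it is unclear whether raw values or residuals were examined.

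The factual part of this stands: the text is incomplete, and neither redaction nor PDF extraction explains it. The consequence does not follow. It goes too far to say that a reader cannot tell which test lies behind a given result, because the markers and the categorical variables each have a stated method. Nobody would take the normality sentence to include categorical variables. The raw-versus-residual distinction largely disappears if the check was made within each arm and time point, since a residual there is the raw value minus a constant; it matters only if arms or times were pooled. Residual plots or a log-scale sensitivity analysis would be a reviewer's preference, as no skew is shown. The model's Time factor "with five levels, with repeated measures" against two described blood draws is a separate matter, and it does not bear on the choice between the t-test and Mann-Whitney.

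**Conclusion.** The concern does not call for a change. The normality sentence and the list of two tests are in tension but compatible, because Mann-Whitney needs no departure from normality to be valid and may serve variables other than those checked. With one test per variable, both procedures keep close to 5% type I error and differ by about 2 to 3 points of power at 23 per arm. Even if both were run on a variable and either counted, which the document does not suggest, the error rate would be about 6%.

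The ambiguity mainly concerns variables other than MMP-2, MMP-9, TIMP-1 and TIMP-2. Filling it in, by naming the variables checked for normality and the test used for each, is ordinary good practice when results are reported. It would not alter any rule, estimate or main analysis. The figures assume equal arms of 23, a two-sided 0.05 level and normal data, as the plan states.

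### The marker ANOVA has five Time levels but the Methods describe two blood samples, and the preoperative marker value is not used as a covariate

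*Combined protocol and SAP*

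**What the plan says.** In the Statistical Analysis Plan: "Data for biological markers were explored within the frame of General Linear Models with the ANOVA method". The model has "one factor between patients (factor 'Group' with two levels) and one factor within patients (factor 'Time' with five levels", with repeated measures. Follow-up is by LSD: "comparisons were done with the Least Significant Difference (LSD) criterion". No covariate is listed. No term of the model and no time point is named as the comparison of desflurane with control.

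In the Methods: "Upon preoperative visit and at 30 minutes post reperfusion blood samples were taken for MMP 2, 9 and TIMP 1, 2 measurement". Histology specimens have their own two times, before inflow occlusion and half an hour after reperfusion.

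The SAP also states, without naming a variable or a time: "Independent samples T-test and independent samples Mann-Whitney test were performed for group (investigation and control) comparisons". The Design section gives the size of the trial, "46 adult patients presented for elective hepatic excision of two or more liver segments", allocated 1:1.

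**The concern.** Two things do not fit.

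First, the stated model needs five measurements per patient, and the described sampling yields two. A reader cannot tell which data enter the analysis, or which degrees of freedom the tests have.

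Second, by the text the preoperative value can enter the ANOVA only as a level of Time. That is an inference, as is reading biological markers to mean the MMPs and TIMPs. If it is right, the model's terms answer different questions. The Group main effect averages the 30-minute value with one taken before any treatment, which treatment cannot change. Group x Time with two times is a test of change from baseline: valid, but generally less precise than an analysis of the 30-minute value adjusted for baseline (ANCOVA). With 46 patients, giving up precision that has already been paid for can decide whether an interval is informative.

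**Working it through.** **1. Count the times.** Stated levels of Time: 5. Marker blood samples in the Methods: 2. Pooling blood and histology times gives 3 distinct times (preoperative visit, before inflow occlusion, 30 minutes after reperfusion). No count gives 5. The Group x Time test would have 1 and 44 degrees of freedom with two times, and 4 and 4 × 44 = 176 with five.

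**2. Inputs for the precision check.** From the Design section: 46 patients, 1:1. Assumed, because the documents do not give them: 23 per arm, two-sided 5% level, normal data, equal SDs at both times, pre/post correlation r = 0.3 / 0.5 / 0.7. Results are in units of the marker's SD. The documents contain no sample-size calculation to reproduce.

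**3. What each two-time term estimates.** Let d be the group difference at 30 minutes, with none expected preoperatively.
- Group main effect: (0 + d)/2 = d/2, with SD √((1 + r)/2). The effect is halved.
- Group x Time: d, with SD √(2(1 − r)). This is the change score.
- 30-minute value alone: d, with SD 1.
- ANCOVA on the preoperative value: d, with variance (1 − r²)(1 + 1/42). The last factor is the price of estimating the slope.

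**4. Variance relative to the 30-minute value alone.**

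| | r = 0.3 | r = 0.5 | r = 0.7 |
|---|---|---|---|
| ANCOVA, (1 − r²)(43/42) | 0.932 | 0.768 | 0.522 |
| Change score, 2(1 − r) | 1.40 | 1.00 | 0.60 |

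**5. Mean 95% CI half-width (SD units).** Unadjusted: 2.015 × 0.994 × √(2/23) = 0.591, where 0.994 is the mean of the sample SD on 44 degrees of freedom. Change score: 0.591 × √(2(1 − r)). ANCOVA: from 100,000 simulated trials per setting.

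| | r = 0.3 | r = 0.5 | r = 0.7 |
|---|---|---|---|
| ANCOVA | 0.570 | 0.518 | 0.427 |
| Unadjusted | 0.591 | 0.591 | 0.591 |
| Change score | 0.699 | 0.591 | 0.458 |

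**6. The same in patients.** To match ANCOVA on 46 patients, the unadjusted comparison needs 46/0.932 = 49, 46/0.768 = 60 or 46/0.522 = 88. The change score needs 46 × 1.40/0.932 = 69, 46 × 1.00/0.768 = 60 or 46 × 0.60/0.522 = 53.

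**7. Power, for illustration only.** The effect of 0.845 SD is an assumption, chosen so that the unadjusted comparison has 80% power. By noncentral t, at r = 0.3 / 0.5 / 0.7: Group main effect 41 / 37 / 33%, Group x Time 66 / 80 / 95%, ANCOVA 83 / 89 / 97%. At r = 0.2 ANCOVA has 80.7%, and at r = 0 it has 79.1%, against 80.0% unadjusted.

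**8. Conditional note on type I error.** In the two-time simulation each test alone rejects 4.9–5.1% under the null. If the better of the Group main effect and Group x Time were picked after seeing results, the rate would be 9.7% per marker; with the 30-minute test also in the choice, 11.0–11.5%.

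**The case against.** The strongest reply is that the covariate is a matter of preference. Leaving it out does not bias a randomized comparison. If the preoperative value is a Time level, the planned model already uses it, and the two-time Group x Time test is valid at 5%. At r = 0.7 its power is within about 2 points of ANCOVA. Below r = 0.2, ANCOVA gains almost nothing over the 30-minute value alone. All of this stands, and it limits the covariate point to precision of unknown size. It does not make the change score the better choice: at r = 0.3 its interval is wider than that of the unadjusted comparison.

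A second reply is that the five levels may belong to other markers or to samples not described. That is possible, but the document names none, so it is a reason to reconcile the sections rather than to leave them.

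A third concerns the unnamed treatment term. A reader might infer that the false-positive rate per marker is therefore about 10–11%. The documents do not support this. The figure holds only if the term was chosen after results were seen, which no section shows. It was also calculated for two times, not the stated five. The SAP says that marker data were explored, so a single confirmatory test may not have been intended. On its own, the unnamed term is a gap in specification.

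Finally, the document is retrospective: it already reports that "All data distributed normally according to Kolmogorov - Smirnov test". A changed analysis is therefore probably post hoc. This also stands.

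**Conclusion.** The point holds in two parts. The mismatch of five Time levels against two blood samples is plain in the text and rests on no assumption about effect or correlation, only on reading the biological markers as the MMPs and TIMPs. As written, the model does not fit the data that the Methods describe.

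The unused covariate is a weaker finding about efficiency. Over the assumed r of 0.3 to 0.7, adjustment shortens the interval by about 4% to 28% against the unadjusted comparison (0.570/0.591 = 0.96; 0.427/0.591 = 0.72). Against the change score it shortens it by about 18% down to 7% (0.570/0.699 = 0.82; 0.427/0.458 = 0.93). These figures depend on 23 per arm, equal SDs and normal data. Since the documents give no r, the actual gain cannot be sized. Nothing here shows bias in the randomized comparison or that a result was selected.

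**What to change.** - State which times form the Time factor, and for which markers, and reconcile this with the two blood samples in the Methods.
- For each marker, fit a linear model of the 30-minute value with group as factor and that marker's preoperative value as covariate. Report the adjusted group difference with its 95% CI as the treatment comparison.
- If further post-treatment times turn out to exist, model the post-baseline values with the preoperative value as covariate and a group-by-time term. The sponsor should name the contrast once the times are settled; the 30-minute contrast should not be imposed before then.
- If data have been examined, label the analysis post hoc and show it beside the stated model. This cannot undo any selection, but it lets the reader compare the two.

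The cost is one degree of freedom per marker and, if r is near zero, about 1 point of power against the unadjusted comparison (79.1% against 80.0% in the illustration). On the two-sample reading no new data are needed, and the model runs in the GLM framework the SAP already uses. Multiplicity across the four markers is not addressed by this change and needs its own rule.

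### The SAP models biological markers over five times, but the Methods give two blood samples for the only markers named, and the five times are listed nowhere

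*Combined protocol and SAP*

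**What the plan says.** The Methods give the blood schedule in one sentence: "Upon preoperative visit and at 30 minutes post reperfusion blood samples were taken for MMP 2, 9 and TIMP 1, 2 measurement". No other marker is named anywhere. The tissue schedule follows: "Specimens for histological test were taken before inflow occlusion and 30 minutes post reperfusion".

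The Statistical Analysis Plan then states: "Data for biological markers were explored within the frame of General Linear Models with the ANOVA method". That model has "one factor between patients (factor 'Group' with two levels" and "one factor within patients (factor 'Time' with five levels, with repeated measures". Means are compared by the LSD criterion. The term biological markers is not defined, and the five levels of Time are not listed.

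The same section also reports: "Independent samples T-test and independent samples Mann-Whitney test were performed for group (investigation and control) comparisons". These tests are not tied to any variable.

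**The concern.** The repeated-measures ANOVA is the only analysis that the SAP assigns by name to biological markers, and MMP-2, MMP-9, TIMP-1 and TIMP-2 are the only markers named. A plain reading therefore puts these four into a five-time model although they have two samples each.

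Three things are left open: which times enter the model, what the Group x Time test compares, and how many means the LSD criterion compares. LSD does not adjust for multiplicity, so the last of these bears on the chance of a false positive. If three further samplings were made and are not described, a reader also could not detect selective reporting by time point.

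The t-test and Mann-Whitney test do not settle the matter, because nothing says that they were the tests used for MMP and TIMP.

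**Working it through.** **Inputs.** Time levels: 5 (Statistical Analysis Plan). Blood times: 2; histology times: 2 (Methods). Groups: 2. Patients: "46 adult patients presented for elective hepatic excision of two or more liver segments, were recruited in the study" (Design). Allocation: "Participants were allocated 1:1 using electronic software" (Design), taken here as 46 / 2 = 23 per group. Complete data are assumed.

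**Step 1: try to reproduce the five levels.**

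| Reading | Times | Count |
|---|---|---|
| Blood only | preoperative visit; 30 min post reperfusion | 2 |
| Histology only | before inflow occlusion; 30 min post reperfusion | 2 |
| Both, distinct times | preoperative visit; before inflow occlusion; 30 min post reperfusion | 3 |

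None gives 5. The stated figure is not reproduced.

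**Step 2: what the number of levels, k, changes.** With N = 46 and 2 groups:

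- Values per marker: N x k. For k = 2, 46 x 2 = 92; for k = 5, 46 x 5 = 230.
- Group x Time degrees of freedom: (k - 1, (46 - 2)(k - 1)). For k = 2, (1, 44), critical F 4.06 at 0.05; for k = 5, (4, 176), critical F 2.42. The five-level figures hold only under sphericity; with two levels the question does not arise.
- Pairwise time comparisons per marker: k(k - 1)/2. For k = 2, 1; for k = 5, 10. Over four markers, 4 against 40.
- Between-group comparisons at each time, per marker: 2 against 5. Over four markers, 8 against 20.
- All pairs of Group x Time cell means, per marker: 4 x 3 / 2 = 6 against 10 x 9 / 2 = 45 (24 against 180 over four markers). This is only an upper bound, since the SAP does not say which means LSD compares.

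As an illustration, ten independent tests at 0.05 would have a family-wise error of 1 - 0.95^10 = 0.40, against 0.05 for one test. Comparisons of repeated measures are correlated, so 0.40 is not an estimate for this trial.

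**Step 3: choices if there are only two times.** With two levels, the Group x Time F test equals the square of the t-test on change from baseline. The alternative is to compare the 30-minute value adjusted for the preoperative value (ANCOVA). The detectable difference was computed from the noncentral t distribution at 23 per group, 80% power and two-sided 0.05. The documents give no pre-post correlation (rho), so a range is shown.

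- 30-minute value alone, 44 df: 0.845 SD.
- Change (Group x Time): 0.845 x sqrt(2(1 - rho)).
- ANCOVA: variance factor 1 - rho^2, 43 df.

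| Assumed rho | Change | ANCOVA | 30-minute value alone |
|---|---|---|---|
| 0.3 | 1.00 SD | 0.81 SD | 0.84 SD |
| 0.5 | 0.84 SD | 0.73 SD | 0.84 SD |
| 0.7 | 0.65 SD | 0.60 SD | 0.84 SD |

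ANCOVA detects the smallest difference in every row.

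**The case against.** The strongest reply is that the SAP never says the five-level model was applied to MMP and TIMP, and the Methods never claim to list every marker. If other markers were measured at five times, the model may be right and the Methods merely incomplete. That is possible, and it is why the point does not claim to know which statement is wrong. It does not remove the problem: the Methods would then omit those markers and their times, and MMP and TIMP would have no stated analysis. The counts over four markers apply only if the model was meant for these four.

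A second reply is that five may be a slip, since a Group-by-Time ANOVA is a valid form with two levels or five. That may be so, but the documents do not show it. The text reports the analysis as already done, so only the sampling record can settle it.

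Third, the gap of 1 against 10 concerns time comparisons, while the trial's question is about groups, where the gap is 2 against 5. This is fair, and both are shown above. The cell-mean bounds include pairs that answer no stated question and should be read only as bounds.

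Fourth, the preference for ANCOVA rests on assumed correlations and is not needed to resolve the inconsistency. That is also correct. A two-level Time model would resolve it and would keep the preoperative sample.

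**Conclusion.** The concern holds. The SAP's only named model for biological markers contradicts the only marker schedule in the document: five levels against two blood times, or three distinct times if histology is added. As described, the data supply 92 of the 230 values per marker that the model needs, and the Group x Time test has (1, 44) rather than (4, 176) degrees of freedom.

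The mismatch itself is a matter of counting and needs no assumption. The sizes assume complete data on 46 patients and, for five levels, sphericity. The detectable differences further assume 23 per group and correlations of 0.3 to 0.7. No bias in a reported result has been shown. The point must be fixed because the marker analysis cannot be reproduced from the plan as written.

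**What to change.** Check the sampling record first, to establish which statement is wrong.

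1. **If MMP and TIMP were sampled only at the two documented times:** set Time to two levels, preoperative and 30 minutes post reperfusion. Test the group effect as Group x Time or, preferably, compare the 30-minute value between groups adjusted for the preoperative value.
2. **If any marker was sampled at five times:** name those markers and list all five times in the Methods, restrict the five-level model to them, and report results at every time. State the analysis of any marker with only two samples separately.

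In both cases, define biological markers, state which means LSD compares, and say which variables the t-test and the Mann-Whitney test apply to. The text is in the past tense, so date the correction and label it post hoc; this matters most if ANCOVA is adopted.

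The cost is a check of existing records and a text correction, with no new patients or samples. Any five-level results already produced for MMP or TIMP must be explained from the sampling record or re-analysed.

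### The repeated-measures ANOVA for the markers keeps only patients with every Time value; a mixed model would use all samples, at low cost and low priority

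*Combined protocol and SAP*

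**What the plan says.** The Statistical Analysis Plan settles three things that matter here.

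- **Software:** "The SPSS v.22.0 software (SPSS, Inc., Chicago, Ill, USA) was utilized for all statistical analyses".
- **Model class:** "Data for biological markers were explored within the frame of General Linear Models with the ANOVA method".
- **Factors:** "one factor between patients (factor 'Group' with two levels", and "one factor within patients (factor 'Time' with five levels, with repeated measures".

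The same section lists independent-samples t-tests and Mann-Whitney tests for comparing the groups. It gives no rule for missing samples, withdrawals or deaths. It defines no analysis set and mentions neither imputation nor a sensitivity analysis.

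On size, the Design section says "46 adult patients presented for elective hepatic excision of two or more liver segments, were recruited in the study" and "Participants were allocated 1:1 using electronic software", which gives about 23 per group (group sizes are not stated). On sampling, the Methods section says: "Upon preoperative visit and at 30 minutes post reperfusion blood samples were taken for MMP 2, 9 and TIMP 1, 2 measurement". That is two draws. The other three Time levels are not identified.

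**The concern.** In an SPSS General Linear Model with a repeated factor, each Time level is normally a column and each patient a row. A row with one empty cell is deleted whole. The choice of method therefore sets a missing-data policy, complete cases only, that the plan never states. Adding a sentence on missing data would not recover the deleted values; the model has to change.

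Two things could be at stake:

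- **Precision.** Samples already collected are left out of the main marker model, in a trial with about 23 patients per group.
- **Selection after randomisation.** If patients with a poor course miss later draws, their earlier values leave the model as well. The comparison then rests on a subset chosen by what happened after allocation.

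The second depends on later draws existing and on patients missing them. The documents show neither.

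**Working it through.** **Inputs from the documents:** 46 patients; 1:1 allocation; Time with five levels in the Statistical Analysis Plan; two draws in Methods.

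**Assumed, because the documents give no figure:** a miss rate m per draw of 2%, 5% or 10%; a within-patient correlation of 0.6; 23 patients per arm. No sample-size calculation is stated, so there is no planned figure to reproduce first.

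**One missed draw.** Planned values per marker are 46 × 5 = 230. With one missed, 229 are observed. The complete-case model uses 45 × 5 = 225 and so discards 4 observed values.

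**Patients dropped, scattered misses.** If draws are missed independently, the share of patients dropped is 1 − (1 − m)^T, where T is the number of Time levels.

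| m | T = 5 | of 46 | T = 2 | of 46 |
|---|---|---|---|---|
| 2% | 9.6% | 4.4 | 4.0% | 1.8 |
| 5% | 22.6% | 10.4 | 9.8% | 4.5 |
| 10% | 41.0% | 18.8 | 19.0% | 8.7 |

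**Patients dropped, monotone dropout.** A patient who dies or withdraws misses every later draw, so the same number of missing samples falls on fewer patients. With a constant small hazard h at each of the four draws after baseline, the average share missing over five draws is about (0 + h + 2h + 3h + 4h)/5 = 2h. Setting 2h = m gives a final dropout of about 4h = 2m, which is 4%, 10% and 20%, or 1.8, 4.6 and 9.2 of 46. Simulation without this approximation gives about 1.9, 4.5 and 8.9.

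**Standard error, scattered misses, five levels.** The simulation (1,500 runs) takes the standard deviation of the estimated group difference in change from baseline. It compares complete-case deletion with generalised least squares on the same samples.

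| m | Time 5: complete-case / all samples | Ratio | Time 3: complete-case / all samples | Ratio |
|---|---|---|---|---|
| 2% | 0.271 / 0.260 | 1.04 | 0.272 / 0.262 | 1.04 |
| 5% | 0.314 / 0.280 | 1.12 | 0.305 / 0.275 | 1.11 |
| 10% | 0.351 / 0.286 | 1.23 | 0.356 / 0.284 | 1.25 |

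Allowing for simulation error, the inflation is about 4%, 10-12% and 23-25%.

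**Standard error, other cases.**

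| Case | m = 2% | m = 5% | m = 10% |
|---|---|---|---|
| Five levels, monotone dropout, same average miss rates | about 1% | 2-3% | 4-7% |

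With two levels and scattered misses, the inflation is about 0.4% to 3% across the three rates. The gain is small there because a patient with only a baseline value says little about change.

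**Limits of the simulation.** The comparator uses the true covariance, whereas a real analysis must estimate it from 46 patients, so the gain is a best case. Missingness is completely at random, so the simulation shows loss of precision and says nothing about bias.

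**The case against.** The case against giving this weight is strong in several respects.

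- **No missing data are documented.** The documents report no withdrawal, death or lost tube. If every sample was obtained, the deletion has no effect. This stands, and the size cannot be set from the documents.
- **The large figures belong to scattered lost samples.** A reader might take 18.8 of 46 patients, or a 23-25% larger standard error, as the cost of death or withdrawal. It is not: at the same average miss rates, monotone dropout costs at most about 4-7%.
- **The described draws leave little to recover.** With two draws the gain is about 0.4-3%. Thirty minutes after reperfusion is also the last draw described, so no described later draw can be missed and take that value with it. The argument about losing early post-reperfusion values applies only to the unidentified Time levels.
- **The deletion is not total.** A reader might infer that all of the patient's marker data are lost to the trial. The t-tests and Mann-Whitney tests need no complete set of times. A failed assay for one marker need not affect the others if the markers are modelled separately.
- **Listwise deletion is inferred.** The plan names a model class and the software, not the exact procedure or data layout. The inference is the ordinary reading, and nothing in the documents overrides it.
- **The plan is written in the past tense.** If the analysis has been done, the change is a re-analysis with a covariance choice made after the data were seen.

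These points lower the priority. They leave the mechanism untouched: the model as specified needs every Time value, and a better method is available in the same software.

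**Conclusion.** The point holds as a cheap improvement of low priority. As specified, any missed draw removes that patient's other values from the repeated-measures model for that marker. The possible cost runs from nothing, if the data are complete, to a standard error about 23-25% larger, if 10% of five draws are lost at random and independently. Those sizes rest on the assumed miss rates, a correlation of 0.6 and a best-case comparator.

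A reader might go further and conclude that the marker comparison is biased towards healthier patients. The documents do not support that: they show no missing samples and no link between illness and missed draws. Selection remains a conditional risk.

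**What to change.** Analyse each marker with a linear mixed model (MIXED in SPSS 22, REML), with Group, Time and Group × Time as fixed effects and a within-patient covariance structure named in advance. Include every randomised patient with any sample, in the assigned group. Keep the repeated-measures ANOVA as a sensitivity analysis, and report the number analysed by group and time for each marker. If the analysis has already been done, declare the mixed model as a re-analysis and say when the covariance structure was chosen.

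The cost is a change of SAP wording and a different procedure in the same package, or a re-run on data already held. The one real downside is the choice of covariance structure. With complete data and compound symmetry, the mixed model gives the same result as the planned ANOVA. Its protection against bias holds only if samples are missing at random, and the report should say so.
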